10.2.2 Modified Psoriasis Area and Severity Index (mPASI)

mPASI Assessments will be performed as follows:

Screening, Baseline, Weeks 4, 12, 24, 36 and 52

Every effort should be made for the same Evaluator to complete the mPASI for the subject at every study visit.

Modified Psoriasis Area and Severity Index (mPASI) is used for the measurement of severity of psoriasis.

mPASI combines the assessment of the severity of lesions and the area affected into a single score in the range 0 (no disease) to 72 (maximal disease).

The body is divided into four sections (head (h) (10% of a person's skin); arms (a) (20%); trunk (t) (30%); legs (l) (40%)). Each of these areas is scored by itself, and then the four scores are combined into the final mPASI. For each section, the percent of area (A) of skin involved is estimated and then transformed into a grade from 0 to 6 (A):

0. 0% of involved area
1. < 10% of involved area - see below for Modified PASI (mPASI) for this grade
2. 10–29% of involved area
3. 30–49% of involved area
4. 50–69% of involved area
5. 70–89% of involved area
6. 90–100% of involved area

mPASI: for subjects with < 10% of an involved anatomic area, the mPASI will be calculated using the actual percentage of the anatomical area involved (e.g. 0.1 for 1%, 0.2 for 2%, 0.3 for 3%, ... 0.9 for 9%), corresponding to the actual percentage of that particular anatomical area of involvement.

Note: Palms and soles may be treated with study medication in this study, but will not be counted towards IGA, mPASI, or BSA assessments.

Within each area, the severity is estimated by three clinical signs: erythema ('E'; redness), induration ('T'; thickness) and desquamation ('S'; scaling). Severity parameters are measured on a scale of 0 to 4, from none to maximum severity possible.

To calculate the mPASI, the sum of the severity rating for the three main signs are multiplied with the numerical value of the area affected and with the various percentages of the four body areas. These values are then added to complete the formula as follows:

$$\text{PASI} = 0.1 (\text{Eh} + \text{Th} + \text{Sh}) \text{Ah} + 0.2 (\text{Ea} + \text{Ta} + \text{Sa}) \text{Aa} + 0.3 (\text{Et} + \text{Tt} + \text{St}) \text{At} + 0.4 (\text{El} + \text{Tl} + \text{Sl}) \text{Al}$$

10.2.3 Body Surface Area (BSA)

BSA Assessments will be performed as follows:

Day 1, Weeks 4, 12, 24, 36, and 52

The BSA affected by psoriasis will be determined by the subject's hand method, where the subject's hand (including fingers) surface area is assumed to equal 1% of body surface area (BSA).

Note: Palms and soles will be treated with study medication, but will not be counted towards IGA or BSA assessments. The scalp is not treated and will not be counted towards any assessments.

10.3 Final Study Visit – End of Study

The final study visit will occur approximately at the end of week 52 of overall involvement in the study. The procedures performed during this visit are as described in [Section 10.1](#) and [Section 10.2](#) and the Schedule of Events for the Week 52 visit ([Section 5](#)). A 7 day scheduling leeway period is allowed for this visit. In addition to the listed procedures to be performed, adverse events will be recorded as reported by the participant or as observed and followed to resolution as necessary (see [Section 10.1.8](#)).

10.4 Early Termination Visit

If a subject is withdrawn or wishes to exit the study, a termination visit will be scheduled. This visit should include the procedures and assessments that would be performed at the final study visit (End of Study visit; see Section 10.3).

10.5 Unscheduled Visit

Subjects that clear between scheduled visits should return for an unscheduled visit for the investigator to confirm IGA, I-IGA (if applicable) and mPASI are clear and subject may stop application of study drug. Unscheduled visits may be necessary for the purpose of measuring time to restarting study drug for those subjects that stopped application of study medication due to resolution of psoriasis plaques. Subjects will call the site when psoriasis returns prior to restarting application of study drug. Unscheduled visits also may be necessary to repeat testing following abnormal laboratory results, for follow-up of AEs, or for any other reason, as warranted in the judgement of the Investigator.

The following information will be collected for all subjects:

- Concomitant medications/procedures
- AEs

The following information will be collected for those subjects that had stopped study medication but are experiencing a reoccurrence of psoriasis plaques:

- Time between stopping study medication and restarting application
- Investigator's Global Assessment (IGA) of psoriasis severity
- Body Surface Area (BSA) of psoriasis involvement (not palms, soles, or scalp)

An updated Body Diagram of psoriasis involvement should be provided to the subject.

The rules for how to tally IGA or other proportions of categorical responses will be described in the Statistical Analysis Plan.

10.6 Adverse Events

10.6.1 Adverse Event Definition

An AE means any untoward medical occurrence associated with the use of a drug in humans, whether or not considered drug related. An AE can therefore be any unfavorable and unintended sign (including an abnormal laboratory finding), symptom, or disease temporally associated with the use of a medicinal (investigational) product, whether or not related to the medicinal (investigational) product.

AEs will be collected following informed consent of the subject through subject study completion.

A treatment emergent adverse event (TEAE) is defined as an AE that started post application of study medication through study completion.

Application site reactions will be considered adverse events if they require intervention, suspension or discontinuation of study drug.

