8 STUDY OBJECTIVE AND ENDPOINTS

8.1 Study Objective

The objective of this study is to assess long-term safety in a multicenter, open-label, 52-week study in subjects treated with ARQ-151 cream 0.3% after completing a 12-week Phase 2b study (ARQ-151-201) Cohort 1 and non ARQ-151-201 subjects (Cohort 2).

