8.2 Study Endpoints

8.2.1 Primary Endpoint

The primary endpoint will be analysis of safety monitored through application site assessments in the clinic using the method of Berger and Bowman, clinical laboratory testing, 12-lead ECGs, PHQ-8, C-SSRS and adverse events. Two primary endpoint analyses are planned:

- Occurrence of Treatment Emergent Adverse Events
- Occurrence of Serious Adverse Events

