10 STUDY PROCEDURES

10.1 Safety Assessments

The Schedule of Visits and Assessments (see [Section 5](#)) summarizes the clinical procedures to be performed at each visit. Individual clinical procedures are described in detail below. Additional evaluations/testing may be deemed necessary by the PI and/or the Sponsor for reasons related to subject safety.

This study assesses the long-term safety of ARQ-151 cream 0.3%. Safety will be monitored through application site assessments in the clinic using the method of Berger and Bowman, physical examination, clinical laboratory testing, 12-lead ECGs, PHQ-8, C-SSRS and AEs as outlined in the Schedule of Visits and Assessments ([Section 5](#)). If deemed necessary, additional safety assessments will be performed at the discretion of the Investigator.

Screening Visit (Cohort 2)

Within 35 days prior to the first dosing, non ARQ-151-201 subjects will be provided details of study requirements and sign an informed consent. Each subject will undergo psoriatic plaque assessments, a physical examination, vital sign measurements (blood pressure, heart rate, and temperature), PHQ-8, C-SSRS, and laboratory tests: hematology, chemistry, urinalysis and a pregnancy test for female subjects of child bearing potential.

Screening should occur for Cohort 1 subjects if they have completed ARQ-151-201 previously.

All screened subjects will receive a screening number and be entered into the electronic subject tracking system.

Day 1 Visit

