10.6.5 Adverse Event Reporting

The PI will review each event and assess its relationship to drug treatment (unrelated, unlikely, possibly, probably, likely). Each sign or symptom reported will be graded on the NIH NCI CTCAE toxicity grading scale 5-point severity scale (Grade 1, 2, 3, 4 and 5). The date and time of onset, time relationship to drug dosing, duration, and outcome (resolved, improved, unchanged, worse, fatal, or unknown/lost to follow-up) of each event will be noted.

The relationship of each AE to the study drug will be assessed using the following definitions:

Unrelated	
 The AE must clearly be caused by the subject's clinical state, or the study procedure/conditions. Definitely not related to drug. Temporal sequence of AE onset relative to administration of drug not reasonable. Another obvious cause of an AE.
Unlikely	
 Time sequence is unreasonable. There is another more likely cause for an AE.
Possibly	
 Corresponds to what is known about the drug. Time sequence is reasonable. Could have been due to another equally, likely cause.
Probably	
 Is a known effect of the drug. Time sequence from taking drug is reasonable. Ceases on stopping the drug.

	
 • Cannot be reasonably explained by the known characteristics of the subject's clinical state.
Likely	
 • Is a known effect of the drug (e.g., listed in Physicians' Desk Reference, Compendium of Pharmaceuticals and Specialties, IB). • Time sequence from taking drug is reasonable. • Event stops upon stopping drug, event returns upon restarting drug.

The following CTCAE toxicity grading scale 5-point severity scale definitions for rating maximum severity will be used:

Grade 1	Mild; asymptomatic or mild symptoms; clinical or diagnostic observations only; intervention not indicated.
Grade 2	Moderate; minimal, local or noninvasive intervention indicated; limiting age-appropriate instrumental activities of daily living.*
Grade 3	Severe or medically significant but not immediately life-threatening; Hospitalization or prolongation of hospitalization indicated; disabling; limiting self-care activities of daily living.** Note: An experience may be severe but may not be serious, e.g., severe headache).
Grade 4	Life-threatening consequences; urgent intervention indicated.
Grade 5	Death related to AE.

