11.1.3 Subjects to Analyze

All analyses will be performed using the Safety Population which includes all subjects who are enrolled and received at least one confirmed dose of ARQ-151 cream 0.15% or ARQ-151 cream 0.3% study medication either in the Phase 2b Study (ARQ-151-201) or this extension study (ARQ-151-202). The number of patients included in the Safety Population will be summarized.

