11.2.1 Adverse Events

All treatment-emergent AEs occurring during the study will be recorded and classified on the basis of MedDRA terminology for the safety population. Treatment-emergent AEs are those AEs with an onset on or after the date of study treatment. All treatment-emergent AEs will be

summarized by scheduled study visit, the number of subjects reporting treatment-emergent AEs, system organ class, preferred term, severity, relationship, and seriousness.

Serious adverse events (SAEs) will be listed by subject. SAEs will be summarized by severity and relationship to study treatment. Each subject will be counted only once within a system organ class or a preferred term using the event with the greatest relationship and greatest severity.

All information pertaining to AEs noted during the study will be listed by subject, detailing the verbatim description given by the Investigator, preferred term, system organ class, start date, stop date, severity, action taken regarding study drug, corrective treatment, outcome, and drug relatedness. The event onset will also be shown relative (in number of days) to date of first application. In addition, a list of subjects who prematurely discontinue from the study due to adverse events will also be provided.

A subject-by-subject treatment-emergent AE (TEAE) data listing, including verbatim term, preferred term, treatment, severity, and relationship to study drug, will be provided.

Medical history will be listed by subject. Physical examinations and 12-lead ECGs will be listed by subject.

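### Both TEAE definitions count onset only, so a pre-dose AE that worsens on 0.3% cream is left out of a primary endpoint

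*Protocol*

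**What the plan says.** **The TEAE rule appears twice.** Section 10.6.1 says a TEAE "is defined as an AE that started post application of study medication through study completion". Section 11.2.1 says "Treatment-emergent AEs are those AEs with an onset on or after the date of study treatment". Neither covers the worsening of an AE that is already present. Neither says whether the application meant is the first in ARQ-151-201 or the first in ARQ-151-202. Section 9.6.3 (reason 2) lists a TEAE and a marked worsening of an AE as separate grounds for removal.

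**Its role.** Under Section 8.2.1, "Two primary endpoint analyses are planned": occurrence of TEAEs and occurrence of SAEs.

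**AE collection.** Sections 10.1.8 and 10.6.1 start collection at consent. For Cohort 2, Section 10.1 says: "Within 35 days prior to the first dosing, non ARQ-151-201 subjects will be provided details of study requirements and sign an informed consent". For Cohort 1, footnote i of Section 5 puts consent after Week 12 of ARQ-151-201.

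**AE recording.** In Section 10.6.5 the CTCAE "5-point severity scale definitions for rating maximum severity will be used". The by-subject AE listing in Section 11.2.1 includes "start date, stop date, severity, action taken regarding study drug, corrective treatment, outcome, and drug relatedness".

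**Population.** Section 11.1.3 uses the Safety Population for every analysis. It contains enrolled subjects who "received at least one confirmed dose of ARQ-151 cream 0.15% or ARQ-151 cream 0.3% study medication either in the Phase 2b Study (ARQ-151-201) or" in the extension itself. The objective in Section 8.1 is long-term safety "in subjects treated with ARQ-151 cream 0.3% after completing a 12-week Phase 2b study" (Cohort 1) and in the newly recruited Cohort 2.

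**The concern.** A treatment-emergent rule usually captures two things: events that start on treatment, and events already present that get worse on treatment. This protocol keeps only the first. Because collection starts at consent, Cohort 2 has a stretch of up to 35 days in which an AE can be recorded before any dose. If such an AE worsens after dosing, its onset date keeps it out of the primary endpoint. The omission works in one direction only: it lowers the TEAE rate.

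Two lesser problems concern the same endpoint. The two definitions do not name the opening dose, and they do not agree on the day of first application. In addition, the population for all analyses can include a rollover whose only active cream, possibly 0.15%, was applied in ARQ-151-201. The reported proportions are then not strictly incidences among subjects treated with 0.3% in this study.

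**Working it through.** The protocol gives no TEAE rate, and Section 11.1.2 states the sample size without a rate or a precision. There is therefore no figure to reproduce. The first two steps set the text side by side. The last two are illustrations in which every rate is an assumption.

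**1. Worsening.** Take a Cohort 2 subject with an AE that starts after consent, before Day 1, and becomes more severe on treatment. Section 10.6.1: it did not start after application, so it is not a TEAE. Section 11.2.1: its onset precedes the treatment date, so it is not a TEAE. It would be counted only if the site entered the worsening as a new AE, and no section asks for that.

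**2. Opening dose and boundary.**
- Evidence for a window in ARQ-151-202: Cohort 1 consents after Week 12 of ARQ-151-201 (Section 5, footnote i), AEs are collected only after consent (Section 10.6.1), and Section 11.2.1 speaks of TEAEs that occur during the study.
- Evidence that the protocol states an anchor when it wants one: the safety baseline is tied to the first active drug across both studies (Section 5, footnote h; Section 10.1, Day 1 Visit; Section 11.1.1 to the same effect). The TEAE rule has no such wording.
- Boundary: cream is applied in the evening (Section 9.8.2). An AE that starts at midday on Day 1 is a TEAE under Section 11.2.1, which compares dates, but not under Section 10.6.1, which requires onset after application.

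**3. Size of the worsening gap, Cohort 2.** Inputs: n = 100 in Cohort 2 and N = 400 in total (Section 11.1.2). Assumed: share a with a pre-dose AE, share w of these that worsens. Subjects missed, at most = n × a × w.

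| a | w | Subjects missed | Points of 400 |
|---|---|---|---|
| 5% | 10% | 0.5 | 0.125 |
| 10% | 20% | 2.0 | 0.5 |
| 15% | 30% | 4.5 | 1.125 |

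These are upper bounds, because a subject with another TEAE is already counted. If 45% have one (assumed), multiplying by 0.55 gives 0.07, 0.28 and 0.62 points.

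**4. Size of the population effect.** Only rollovers who had active cream in ARQ-151-201 can enter the Safety Population without a dose in ARQ-151-202; vehicle rollovers and Cohort 2 need one. Such subjects are conceivable: Section 9.1 allows 0% BSA, and Section 11.3 allows for prior-active rollovers who need no further treatment. Assumed: 150 or 200 of the 300 Cohort 1 subjects are prior-active, 1%, 5% or 10% of these are never dosed in ARQ-151-202, and the TEAE rate among dosed subjects is p = 45%. With a window in ARQ-151-202, undosed subjects have no TEAE, so the shift is −d × p, with d = undosed / 400.

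| Prior-active | Undosed | d | Shift in TEAE rate (points) |
|---|---|---|---|
| 150 | 1.5 / 7.5 / 15 | 0.375% / 1.875% / 3.75% | −0.17 / −0.84 / −1.69 |
| 200 | 2 / 10 / 20 | 0.5% / 2.5% / 5% | −0.23 / −1.13 / −2.25 |

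For SAEs with d = 5%, a rate of 1% to 5% among dosed subjects, and no SAE among the undosed, the shift is −0.05 to −0.25 points. Section 8.2.1 does not limit SAEs to treatment-emergent ones, so SAEs in undosed subjects may count, which would reduce this dilution. The onset rule does not affect SAEs at all.

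**The case against.** The case for leaving the text alone has substance.

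- **The window is largely settled by context.** Consent timing and collection from consent point to events in ARQ-151-202. A reader might infer that the TEAE window could run from the first ARQ-151-201 dose and cover 64 weeks (12 + 52) for prior-active rollovers. The documents do not support that as the planned count: AEs in this study are collected only after a consent signed at the end of ARQ-151-201. What stands is that the opening dose should be named and the boundary made consistent.
- **Worsening may be captured in practice.** A psoriasis flare is expressly an AE (Section 10.1.8), the AE definition is broad, and Section 10.6.2 exempts only admissions for pre-existing conditions that have not worsened. It is tempting to add vehicle rollovers whose ARQ-151-201 events worsen on 0.3% cream. That does not follow: those conditions predate AE collection in this study, and a later worsening could be entered as a new AE with a new onset. The firm case is an AE that starts between consent and first dose, chiefly in Cohort 2.
- **The data may allow reclassification.** The listing in Section 11.2.1 names no date of worsening, and one might conclude that such events could never be recovered. The CRF is not shown and that section promises all AE information, so the conclusion goes too far. It remains true that the protocol does not require the date.
- **The population may be deliberate.** It matches the cross-study safety baseline, Section 9.3 makes treatment the default, and Section 11.1 lets percentage denominators fit the purpose of the analysis. This reduces the population issue to a secondary one.
- **The study is descriptive.** It is single-arm, with no formal inference on safety (Section 11.2). That limits the consequence, but TEAE incidence is still a primary result.

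The SAP is not at hand and may refine these rules. The onset-only rule is nevertheless fixed in the protocol, in two places.

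**Conclusion.** The point holds. As written, an AE that begins after consent but before the first application in ARQ-151-202 and then worsens on 0.3% cream is not a TEAE. This can only lower the rate. Its size cannot be derived from the protocol; it is probably about 1 percentage point or less of 400, on the assumption that 5% to 15% of Cohort 2 have a pre-dose AE and 10% to 30% of those worsen.

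The opening dose is unnamed and the two definitions differ at the boundary, although context favours ARQ-151-202. The inclusion of rollovers never dosed in ARQ-151-202 is a secondary, edge-case matter: a dilution of about 0.2 to 2.25 points under the assumed shares, and possibly a deliberate choice. This is a definition worth correcting because the correction is cheap and the endpoint is primary. It does not show that the study's safety conclusions would be wrong.

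**What to change.** 1. Use one definition in Sections 10.6.1 and 11.2.1: an AE with onset, or with worsening in severity or seriousness, on or after the first 0.3% application in ARQ-151-202, through study completion.
2. Instruct sites to record the worsening of a pre-dose AE with its own start date. This part is the most time-critical, since a later analysis plan cannot readily recover dates that sites were never asked to record.
3. Report TEAE and SAE incidence among subjects with at least one application in ARQ-151-202. Show separately the events in enrolled subjects not dosed in ARQ-151-202, and events before the first application there, so that none is lost.
4. Keep the Section 11.1.3 population for the treatment-free-days analysis and as a supplementary summary.

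The cost is wording in the definition and population sections, one recording instruction, and one extra table with its denominator. The TEAE rate may come out slightly higher. The TEAE anchor would also differ from the cross-study baseline used for changes in other safety measures, and the report should say so.

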10.6.2 Serious Adverse Event

The definitions and reporting requirements of Health Canada/the Food and Drug Administration (FDA)/ICH Guidelines for Clinical Safety Data Management, Definitions and Standards for Expedited Reporting, Topic E2A will be adhered to. If any AEs are serious, as defined by ICH Guidelines for Clinical Safety, required procedures will be followed. All SAEs will be reported to the Sponsor via fax or e-mail within 24 hours of becoming aware of the event, whether or not the serious events are deemed drug-related. All serious event reporting will adhere to ICH E6: Guideline for Good Clinical Practice and ICH E2A: Clinical Safety Data Management: Definitions and Standards for Expedited Reporting.: The ERB/IRB will be notified of the Alert Reports as per HC, FDA, ICH and the IRB/ERB's policies and procedures.

An SAE is any AE that in the view of either the PI or Sponsor, results in any of the following outcomes: Death, a life-threatening AE, inpatient hospitalization or prolongation of existing hospitalization, a persistent or significant incapacity or substantial disruption of the ability to conduct normal life functions, or a congenital anomaly/birth defect. Important medical events that may not result in death, be life-threatening, or require hospitalization may be considered serious when, based upon appropriate medical judgment, they may jeopardize the subject and may require medical or surgical intervention to prevent one of the outcomes listed in the above definition. Examples of such medical events include allergic bronchospasm requiring intensive treatment in an emergency room or at home, blood dyscrasias or convulsions that do not result in inpatient hospitalization, or the development of drug dependency or drug abuse.

Life-threatening is defined as an AE that in the view of the PI or Sponsor, places the subject at immediate risk of death. It does not include an AE that, had it occurred in a more severe form, might have caused death.

Hospitalization does not include the following:

- Rehabilitation facilities, hospice facilities or respite care (e.g. caregiver relief)
- Nursing homes or skilled nursing facilities
- Emergency room visits
- Same day surgeries (as outpatient/same day/ambulatory procedures)
- <24 hour admissions for observation or evaluation

Hospitalization or prolongation of hospitalization in the absence of a precipitating, clinical AE is not in itself an SAE. Examples include:

- Admission for treatment of a preexisting condition that did not worsen
- Hospitalizations for cosmetic elective surgery, social, and/or convenience admissions
- Pre-planned treatments or surgical procedures should be noted in the history documentation for the individual subject.
- Diagnostic and therapeutic procedures, such as surgery, should not be reported as AEs; however, the medical condition for which the procedure was performed should be reported if it occurs during the reporting period and meets the definition of an AE. For example, an acute appendicitis that begins during the AE reporting period should be reported as an AE, and the resulting appendectomy should be recorded as treatment of the AE.

Unexpected is defined as an AE that is not listed in the IB or is not listed at the specificity or severity that has been observed; or is not consistent with the risk information described in the general investigational plan or elsewhere in the current IND/CTA.

If a SAE occurs to a subject on this study, contact the Sponsor personnel listed in [Section 2](#) within one business day of knowledge of event.

